## 7.8 Efficacy Analysis

ORR, CR and PR rates, DOR, PFS, and OS will primarily be conducted using the safety/mITT population. Sensitivity analyses of the efficacy endpoints including ORR, CR and PR rates, and DOR will also be evaluated using the Per-protocol population. All efficacy data will be summarized by disease type outlined in Section 7.1.

### 7.8.1 Primary Efficacy Endpoint(s)

The primary efficacy endpoint is the ORR of patients who achieve a CR or PR as determined by the investigator using PET scans, CT scans, and clinical assessment according to IWG revised response criteria.

ORR per investigator (CR+PR) will be summarized with 2-sided 95% exact confidence intervals using the safety/mITT population. A sensitivity analysis of ORR per investigator will also be summarized using the Per-protocol population.

The sum of products of diameters (SPD) for up to 6 of the largest dominant nodes or nodal masses will be quantitatively identified at baseline and subsequent response assessments. A waterfall plot will be used to characterize the best percent change of SPD from Baseline in target lesions for individual patients.

No formal hypothesis testing will be conducted with respect to ORR.

### 7.8.2 Secondary Efficacy Endpoint(s)

CR rate per investigator will be summarized with 2-sided 95% exact confidence intervals using the safety/mITT population. A sensitivity analysis of CR rate per investigator will also be summarized using the Per-protocol population

DOR and PFS will be estimated base on the investigator assessments using PET scans, CT scans, as well as clinical evaluations according to the IWG revised response criteria. DOR will primarily be summarized using the subset of patients with a CR or PR in the safety/mITT population; a sensitivity analysis of DOR will also be summarized using the subset of patients with a CR or PR in the Per-protocol population. PFS and OS will be summarized using the safety/mITT population.

DOR in subjects with a CR or PR is defined as the time from start of the first documentation of objective tumor response (CR or PR) to the first subsequent documentation of objective tumor progression or to death due to any cause, whichever comes first. DOR will be censored on the day of the last assessment of measured lesions documenting absence of PD for patients who do not have objective tumor progression and are still on study at the time of analysis, are given antitumor treatment other than the study treatment or SCT, or are removed from study prior to documentation of objective tumor progression.

PFS is defined as the time from the first dose until disease progression or death due to any cause, whichever occurs first. PFS will be censored on the day of the last assessment of measured lesions documenting absence of PD for patients who do not have objective tumor progression and are still on study at the time of analysis, are given antitumor treatment other than the study treatment or SCT, or are removed from study prior to documentation of objective tumor progression. Patients lacking an evaluation of tumor response after their first dose will have their event time censored at the day of first dose.

OS is defined as the time from the first dose until death due to any cause. In the absence of confirmation of death, survival time will be censored at the last date the patient is known to be alive. Patients lacking data beyond the day of first dose will have their survival time censored at the day of first dose.

DOR, PFS, and OS will be analyzed using the Kaplan-Meier method, the 25th, 50th (median), and 75th percentiles, if estimable, will be presented along with the associated 2-sided 95% confidence intervals. The results will also be presented in figures (Kaplan-Meier plots).

For patients with any B symptom at Baseline, B symptom resolution rate and the 95% exact CI will be summarized.

Efficacy data will also be listed by patient.

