Primary Objectives: To evaluate the efficacy and the safety of brentuximab vedotin in Chinese patients with relapsed/refractory CD30+ HL or sALCL.				
Secondary Objectives: To evaluate the PK and immunogenicity of brentuximab vedotin in Chinese patients with relapsed/refractory CD30+ HL or sALCL.				
Subject Population: Chinese patients aged 18 years or older with relapsed/refractory CD30+ HL or sALCL.				

Number of Subjects: Approximately 30 subjects (HL, approximately 22 subjects; sALCL, approximately 8 subjects).	Number of Sites: Approximately 7 sites.
Dose Level(s): Brentuximab vedotin, 1.8 mg/kg, administered on Day 1 of each 21-day cycle.	Route of Administration: IV
Duration of Treatment: A maximum of 16 cycles (Approximately 12 months).	Period of Evaluation: Approximately 30 months, including 18 months of long-term follow-up.
Main Criteria for Inclusion:	

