## **7.0 STUDY DESIGN**

### **7.1 Overview of Study Design**

This is a single-arm, open-label, multicenter, phase 2 study designed to evaluate the efficacy, safety, and PK of brentuximab vedotin as a single agent in Chinese patients with relapsed/refractory CD30+ HL or sALCL. Brentuximab vedotin will be administered as a single, 1.8 mg/kg IV infusion on Day 1 of each 3-week cycle.

Patients will receive a maximum of 16 cycles if they do not meet the criteria for removal from the study. Patients will be assessed for overall response using the Revised Response Criteria for Malignant Lymphoma [1]. Dedicated computed tomography (CT) scans (neck, chest, abdomen, and pelvis) will be performed at Baseline and at Cycles 2, 4, 7, 10, 13, and 16, and positron emission tomography (PET) scans will be performed at Baseline and at Cycles 4 and 7. No additional PET scanning is required beyond Cycle 7 unless clinically indicated. B symptoms will be assessed at Baseline and on Day 1 of each cycle.

Patients may continue on study treatment until the sooner of disease progression, unacceptable toxicity, or completion of 16 cycles. Patients, including those who discontinue study treatment for any reason other than withdrawal of consent, will have safety follow-up assessments through 30 days after the last dose of study drug (end of treatment [EOT]). Patients who discontinue study treatment with stable disease (SD) or better will be followed for PFS until disease progression, death, withdrawal of consent, or initiation of a new treatment, whichever occurs first. A CT scan will be performed every 12 weeks for the first 12 months and at 18 months after EOT. Patients will be followed for OS every 12 weeks until death, withdrawal of consent, or study closure, whichever occurs first. All patients will have the opportunity to be followed for 18 months after EOT. The study will be closed when all patients enrolled have completed the required follow-up.

Toxicity will be evaluated according to the National Cancer Institute Common Terminology Criteria for Adverse Events (NCI CTCAE), version 4.03, effective 14 June 2010 [2]. Laboratory values, vital signs, and electrocardiograms (ECGs) will be obtained to evaluate the safety and tolerability of brentuximab vedotin. Serial blood samples for determination of the serum/plasma concentration and immunogenicity of brentuximab vedotin will be obtained at prespecified time points as described in Table B in [Appendix A](#).

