### **7.3 Duration of Study**

The screening period will be up to 4 weeks, and the treatment period will be up to 16 cycles (approximately 12 months). Patients will have safety follow-up assessments through 30 days after the last dose of brentuximab vedotin. All patients who discontinue brentuximab vedotin for any

reason other than withdrawal of full consent will undergo a long-term follow-up every 12 weeks after the safety follow-up assessments. Patients will be followed until all patients have had the opportunity to be followed for 18 months after EOT. The study will be closed when all patients enrolled have completed the required follow-up. It is expected that the study will last approximately 3.5 years.

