## **10.9 Long-term Follow-up Assessments**

Patients who discontinue study treatment with SD or better will be followed for PFS until disease progression, death, withdrawal of consent, or initiation of a new treatment, whichever occurs first. A CT scan will be performed every 12 weeks ( $\pm 14$  days) for the first 12 months and at 18 months after the EOT. Patients will be followed for OS every 12 weeks ( $\pm 14$  days) until death, withdrawal of consent, or study closure, whichever occurs first. Survival information may be collected by methods including, but not limited to, telephone, e-mail, or mail. Patients will be followed until all patients have had the opportunity to be followed for 18 months after EOT. The study will be closed when all patients enrolled have completed the required follow-up.

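### PFS and DOR censor living patients at their last scan but count later events without limit, so one late event can take the final Kaplan-Meier tail to zero

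*SAP*

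**What the plan says.** **Events.** SAP 7.8.2: "PFS is defined as the time from the first dose until disease progression or death due to any cause, whichever occurs first". DOR ends at the "first subsequent documentation of objective tumor progression or to death due to any cause, whichever comes first". Neither definition limits how long after the last scan an event may fall.

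**Censoring.** SAP 7.8.2: "PFS will be censored on the day of the last assessment of measured lesions documenting absence of PD". This covers patients without progression who are still on study, who start antitumor treatment other than study drug or SCT, or who leave the study. DOR uses the same rule. The date is the last lesion assessment, not last contact or data cutoff.

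**Scans.** Protocol 7.1: "A CT scan will be performed every 12 weeks for the first 12 months and at 18 months after EOT". No later scan is scheduled. Protocol 10.3.14 also asks for imaging when symptoms suggest progression, where possible, and sets no end date for this.

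**Survival follow-up.** Protocol 7.1: "Patients will be followed for OS every 12 weeks until death, withdrawal of consent, or study closure, whichever occurs first". Protocol 10.9: "Patients will be followed until all patients have had the opportunity to be followed for 18 months after EOT". Closure therefore waits for the last patient.

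**Outputs.** SAP 7.8.2 plans Kaplan-Meier plots and the 25th, 50th and 75th percentiles. Under SAP 7.1 the primary analysis comes once all patients could have had 16 cycles and EOT assessments. The final analysis, in the CSR addendum, comes once all could have been followed for 18 months after EOT.

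**The concern.** Kaplan-Meier estimation requires that being at risk at time t does not depend on what happens after t. Here it does. Take two patients who are progression-free at the same final CT. The one who lives is removed at that CT. The one who later dies, or has progression found on an unscheduled scan, stays at risk until that event.

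Beyond the last scheduled scans, the risk set is therefore made up of patients selected because they go on to have an event. This pushes the tail down. With about 22 HL and 8 sALCL patients, one late event can turn a plateau of durable responders into an apparent 100% event rate. It can also turn a percentile that should be reported as not reached into a specific number of months.

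**Working it through.** **1. The plan's own figures.** The only probability statement in the plan concerns ORR. P(X ≥ 9 | n=22, p=0.65) = 99.42% and P(X ≥ 5 | n=8, p=0.80) = 94.37%, which agree with the stated >99% and >94%. The plan gives no PFS, DOR or late-death rate to reproduce.

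**2. How long the event-only window lasts.**
- Sixteen undelayed 21-day cycles put the last dose 15 × 21 = 315 days after the first, that is 315/30.4375 = 10.3 months.
- The last scheduled CT is then at 10.3 + 18 = 28.3 months if EOT is the last dose. If EOT is 30 days later, it is at 345/30.4375 + 18 = 29.3 months.
- Protocol 7.3: "It is expected that the study will last approximately 3.5 years", so about 42 months. For the first patient enrolled the window is 42 − 29.3 = 12.7 to 42 − 28.3 = 13.7 months. It is up to 28/30.4375 = 0.9 month less if the 42 months include that patient's screening.
- Protocol 2.0 gives a period of evaluation of "Approximately 30 months, including 18 months of long-term follow-up". This implies about 42 − 30 = 12 months of accrual.
- The last enrolled completer has a window of about zero, because that patient's follow-up sets closure. Patients who stop early without progression can have more than 13 months.

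**3. Worked HL example (assumed data, n=22).** Thirteen events by month 24, eight patients alive and progression-free with last scan at 29.4 months, one death at month 36.
- After month 24: S = 9/22 = 0.409.
- At month 36 as written: risk set 1, so S = 0.409 × (1 − 1/1) = 0. The 75th percentile is reported as 36 months.
- With aligned follow-up: the curve ends at 0.409 and the 75th percentile is not reached.
- For comparison, with the eight living patients kept at risk: S = 9/22 × 8/9 = 8/22 = 0.364.

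**4. Worked sALCL example (assumed data, n=8).** Three events by month 12, four censored at 29.4 months, one death at month 36. S = 5/8 = 0.625 before the death and 0 after it as written, against 5/8 × 4/5 = 0.500 with the others kept at risk. As written, the median is also reported as 36 months. With aligned follow-up the curve stays at 0.625 and the median is not reached.

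**5. How often: simulation under assumed rates.** Assumptions: 12-month accrual, all final scans at 29.4 months ± 14 days, median 6 or 12 months to progression among progressors, 20-50% never progressing, and a 3-10% annual risk of death. No early stoppers, new therapy or post-scan imaging are modelled. The aligned rule here censors deaths after the final scan at that scan. There were 3,000 to 4,000 runs per scenario.

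| Result | As written | Aligned |
|---|---|---|
| HL, curve reaches 0 | 7-39% | 0-2% |
| sALCL, curve reaches 0 | 6-29% | 0.4-22% |
| HL with 50% never progressing, 75th percentile reached | 17-41% | 1-3% |
| HL with 50% never progressing, median reached | 51-87% | 40-75% |

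The high aligned figure for sALCL comes from genuine events. If 20% never progress, all eight are progressors with probability 0.8^8 = 0.168. Where only 20% of HL patients never progress, the 75th percentile is usually reached either way (73-87% as written, 70-82% aligned).

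**6. Late progressions.** A second simulation, on different assumed rates, puts HL curves at 0 in about 20-29% of cohorts as written. If symptom-driven imaging documents 50-80% of post-scan progressions, a rule that removes late deaths only still leaves about 12-21%. One common cutoff for progression and death leaves about 1%.

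**The case against.** **Progression can still be seen late.** A reader might infer that nothing but death can count after the 18-month CT. The documents do not support that. Protocol 10.3.14 asks for imaging of suspicious symptoms without an end date, and SAP 7.8.2 also uses clinical evaluations. This corrects the mechanism but does not remove it. A late progression counts as an event while living patients who are not rescanned stay censored earlier, so the tail falls in the same way.

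**Some late deaths drop out.** Patients who start antitumor therapy other than SCT are censored, so their later deaths should not count. This stands and lowers the frequency. Deaths after SCT still count.

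**Follow-up may end at 18 months.** Protocol 10.5 could be read as ending participation at that point. Protocol 7.1, 7.3, 10.9 and the Appendix A footnote on survival follow-up all run to closure. The passages should be reconciled.

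**Counting every death follows the protocol.** Protocol 14.1.3 defines PFS and DOR with death from any cause. Removing late events departs from that and can favour the drug if those patients had progressed unseen. This stands, and it is why the all-events analysis should be kept as a sensitivity analysis.

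**It would be visible.** Confidence intervals, plots, listings and the percentage censored would show a percentile resting on one patient. That helps a careful reader, but the reported figure would still be wrong in kind.

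**Conclusion.** The concern holds for the tail of PFS and DOR at the final analysis. Following SAP 7.8.2 exactly makes membership of the late risk set depend on a later event, and one such event after every other patient's last scan takes the curve to 0. The 75th percentile is most exposed. The median is exposed too if about half the cohort stays progression-free. Early percentiles are little affected.

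The frequency is uncertain. The documents give no PFS or post-scan death rates, so the 7-39% and 20-29% for HL show that the effect is not negligible and do not predict it. A reader might infer that the curve will usually fall to zero; neither range supports that. The effect is smaller where late events overlap with other patients still being scanned.

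A reader might also infer that the trial's main efficacy result is at risk. It is not. ORR and the sample size do not use this rule. With about 12 months of accrual, the primary analysis falls at about month 24, before any 16-cycle completer reaches a final CT at 28.3 months or later. Only patients who stopped early without progression could be affected by then.

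**What to change.** In SAP 7.8.2, set one end of PFS and DOR observation for both components: each patient's 18-month post-EOT CT visit plus its 14-day window. Progression or death up to that date is an event. A patient whose first progression or death comes later is censored at the last tumor assessment on or before that date. The other censoring rules and OS stay as they are. Report the all-events version as a sensitivity analysis.

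State which date EOT means for this cutoff. Protocol 2.0 attaches EOT both to the last dose and to the safety follow-up 30 days later, and that difference exceeds the 14-day window.

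The cost is one sentence and one date comparison in programming, with no new data. The downsides should be stated in the SAP. A few late events leave PFS and DOR, which can make the curves look more favourable if those patients had progressed unseen. Upper percentiles may be not estimable. A smaller asymmetry remains between the 12- and 18-month scans: a death in that gap counts, while a living patient without the later scan is censored at the earlier one. The rule should be fixed before late events are known, so that the choice is not made after seeing them.

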## **8.0 STUDY POPULATION**

### **8.1 Inclusion Criteria**

Each patient must meet all of the following inclusion criteria to be enrolled in the study:

1. Male or female Chinese patients aged 18 years or older at the time of informed consent.
2. Patients must have histologically confirmed CD30+ HL or sALCL. Immunohistochemistry or flow cytometry may be performed on either original diagnostic biopsy material or biopsy of relapsed disease, and pathology reports of CD30+ or their copies should be retained at the site.
3. Patients with CD30+ HL or sALCL who have relapsed from or are refractory to previous treatments.
4. Fluorodeoxyglucose (FDG)-PET positive and measurable disease of at least 1.5 cm in the longest diameter by CT, as assessed by the site.
5. Patients must have an Eastern Cooperative Oncology Group (ECOG) performance status of 0 or 1.
6. Voluntary written consent must be given before performance of any study-related procedure not part of standard medical care, with the understanding that consent may be withdrawn by the patient at any time without prejudice to future medical care.
7. Female patients who:
  - Are postmenopausal for at least 1 year before the screening visit, OR
  - Are surgically sterile, OR
  - If they are of childbearing potential, agree to practice 2 effective methods of contraception, at the same time, from the time of signing the informed consent through 6 months after the last dose of study drug.

Male patients, even if surgically sterilized (ie, status postvasectomy), who:

- Agree to practice effective barrier contraception during the entire study treatment period and through 6 months after the last dose of study drug.

8. Suitable venous access for the study-required blood sampling, including PK sampling.
9. Patients must have the following required screening laboratory data. Patients must not have received recombinant granulocyte-colony stimulating factor (G-CSF) or platelet transfusion within 1 week before the screening hematology assessment.
  - Absolute neutrophil count  $\geq 1500/\mu\text{L}$ .
  - Platelet count  $\geq 75,000/\mu\text{L}$ .
  - Serum bilirubin level  $\leq 1.5$  times the upper limit of the normal range (ULN).
  - Serum creatinine level  $\leq 1.5$  times the ULN.

- Alanine aminotransferase (ALT) and aspartate aminotransferase (AST)  $\leq 2.5$  times the ULN.
- 10. Survival for 3 or more months must be expected.

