### **10.3.14 Disease Assessment**

Tumor response will be evaluated according to the Revised Response Criteria for Malignant Lymphoma [\[1\]](#).

All imaging will be performed with contrast, except for subjects in whom contrast imaging is difficult because of hypersensitivity to contrast medium, bronchial asthma, renal impairment, or other conditions.

Measurable lesions are those that meet all the following criteria:

- Lymph nodes diagnosed as lymphoma lesions, or nodular masses involving extranodal organs on CT imaging.
- Lesions that can be accurately measured in 2 perpendicular directions on CT cross-sectional images.
- Lesions with longest diameter  $\geq 1.5$  cm on CT cross-sectional images.
- FDG-PET positive lesions.

As many as 6 target lesions will be selected among the measurable lesions, whether nodal or extranodal, in order of decreasing longest diameter on CT cross-sectional images.

B symptoms will be assessed at prespecified time points as described in the Schedule of Events ([Appendix A](#)).

Bone marrow aspirate or biopsy will be performed within 2 weeks before the first dose of brentuximab vedotin (it is not necessary to repeat these procedures in patients with a positive bone marrow aspirate or biopsy performed after the most recent antineoplastic therapy). For patients with bone marrow involvement at Baseline, bone marrow aspirate or biopsy is required to confirm the CR status. Bone marrow aspirate or biopsy samples will be collected within 2 weeks after CT scans. Further bone marrow assessments are not required after bone marrow aspirate or biopsy becomes negative.

Timing of CT scans will be as follows:

- Screening period: Days -28 to 0.
- Cycles 2, 4, 7, 10, 13, and 16: Days 15 through 21 (before study treatment in the next cycle).

Subjects who discontinue study treatment or assessments for the reasons stated in Section 10.6 other than progressive disease (PD) and have not undergone assessment within the past 6 weeks should have tumor response assessed during the safety follow-up whenever possible.

Subjects who discontinue study treatment for any reason other than PD will have CT scans every 12 weeks ( $\pm$ 14 days) for the first 12 months and at 18 months after EOT until disease progression, death, withdrawal of consent, or initiation of a new treatment, whichever occurs first.

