## **10.6 Discontinuation of Treatment With Study Drug and Patient Replacement**

Treatment with study drug may be discontinued for any of the following reasons:

- AE.
- Protocol violation.
- PD.
- Study terminated by sponsor.
- Withdrawal by subject.
- Lost to follow-up.
- Administrative decision by the investigator/subinvestigator or the sponsor.
- Pregnancy.
- Completed 16 cycles of treatment at response (CR or PR) or SD.
- Initiation of subsequent stem cell transplant
- Other.

Once study drug has been discontinued, all study procedures outlined for the safety follow-up visit will be completed as specified in the Schedule of Events ([Appendix A](#)). The primary reason for study drug discontinuation will be recorded on the eCRF.

Reasons that may cause a subject to be replaced include but are not limited to:

- Patient does not meet Inclusion Criterion 2.
- Patient has not taken at least 1 dose of brentuximab vedotin.
- Patient is not response evaluable according to the Revised Response Criteria for Malignant Lymphoma [1].

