**CONFIDENTIAL**

- DOR, defined as the time between the first documentation of objective tumor response (CR or PR) and the first subsequent documentation of objective tumor progression or death due to any cause, whichever occurs first.
- PFS, defined as the time from the start of study treatment to the first documentation of objective tumor progression or to death due to any cause, whichever occurs first.
- OS.
- B symptom resolution rate.

Pertinent variables will be summarized descriptively. Continuous variables will be summarized, including the number of subjects, mean, standard deviation, median, minimum, and maximum values; for categorical variables, the frequency and percentage per category will be summarized. Two-sided exact 95% CIs will be computed using appropriate techniques for ORR and CR.

Time-to-event variables will be summarized by the Kaplan-Meier method with the associated 95% CIs when estimable.

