## 7.0 METHODS OF ANALYSIS AND PRESENTATION

### 7.1 General Principles

In general, descriptive statistics (number of observations, mean, standard deviation [StdDev], median, minimum, and maximum) will be used to summarize continuous variables. Frequency and percentage will be used to summarize categorical variables. Time-to-event data will be analyzed using the Kaplan-Meier method and results will be summarized by the 25th, 50th (median), and 75th percentiles, if estimable, with associated 2-sided 95% confidence intervals, as well as the percentage of censored observations.

Means and medians will be presented to 1 more decimal place than the recorded data. The standard deviations (StdDev) will be presented to 2 more decimal places than the recorded data. Confidence intervals about a parameter estimate will be presented using the same number of decimal places as the parameter estimate.

Unless otherwise specified, safety and efficacy data will be summarized in the following 3 groups: patients with r/r HL only, patients with r/r sALCL only, all patients. Analyses pertaining to pharmacokinetics and immunogenicity will be summarized by treatment cycle at the prespecified time points.

The baseline value is defined as the value collected at the time closest to, but prior to, the start of study drug administration, unless otherwise specified. A windowing convention may be used to determine the analysis value for a given study visit for observed data analyses.

All available efficacy and safety data will be included in data listings and tabulations. Data that are potentially spurious or erroneous will be examined under the auspices of standard data management operating procedures. In general, there will be no imputation of missing data. For time-related endpoints, subjects who have no specified events will be censored as specified for each respective endpoint in Section 7.8. Imputation rules for missing dates of AEs and concomitant medications are detailed in Sections 7.1.3 and 7.1.4.

The primary analysis for the clinical study report including the primary and the secondary endpoints will be conducted when all patients have had the opportunity to receive 16 cycles of treatment and have had EOT assessments. The results will be summarized in the primary CSR. The final analysis will be conducted when all patients have had the opportunity to be followed for 18 months after EOT. These results will be summarized in the CSR Addendum.

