## 7.2 Analysis Sets

### 7.2.1 Safety/Modified Intent-to-Treat Population

The safety/modified intent-to-treat (mITT) population consists of all subjects who have measurable lesions at Baseline and receive at least 1 dose of brentuximab vedotin. The safety/mITT population will be used for analyses of efficacy, safety, and patient demographics and baseline disease characteristics, unless otherwise stated.

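### The SAP's fallback censoring sentence for PFS makes no exception for death: a minor wording conflict with the PFS definition

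*SAP*

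**What the plan says.** SAP 7.8.2 gives the definition: "PFS is defined as the time from the first dose until disease progression or death due to any cause, whichever occurs first". Protocol 14.1.3 agrees, running PFS from the start of treatment "to the first documentation of objective tumor progression or to death due to any cause".

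The SAP's PFS paragraph then sets two censoring rules.

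- Patients without objective progression who are still on study, have received antitumor treatment other than study drug or SCT, or have left the study are censored at their last lesion assessment showing no progression.
- The closing sentence is the fallback: "Patients lacking an evaluation of tumor response after their first dose will have their event time censored at the day of first dose".

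SAP 7.1 states the general principle: "subjects who have no specified events will be censored as specified for each respective endpoint in Section 7.8".

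PFS is analysed in the safety/mITT population, which "consists of all subjects who have measurable lesions at Baseline and receive at least 1 dose of brentuximab vedotin". No post-baseline evaluation is required. The OS rule in the same section is worded differently: its censoring applies only where death has not been confirmed.

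**The concern.** The only condition in the fallback is a missing tumor evaluation. A dosed patient who dies before being evaluated therefore meets the event definition and, on the literal words, the censoring rule as well. The patient cannot drop out through the analysis set, because mITT membership needs only measurable baseline lesions and one dose.

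If 7.8.2 were programmed sentence by sentence, that death would leave the risk set at time zero and would never lower the PFS curve. The planned outputs exposed are the Kaplan-Meier percentiles and plots for PFS, reported for HL, sALCL and all patients. One patient weighs most in the sALCL cohort of about 8.

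**Working it through.** **Plan's own figures.** The plan states no PFS figure. Its only design probabilities concern ORR. They reproduce: P(at least 9 of 22 responses at 65%) = 0.9942 and P(at least 5 of 8 at 80%) = 0.9437, against the stated >99% and >94%. They do not bear on this point and would not change.

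**When a patient can be unevaluated.** Protocol 10.3.14 places the first on-treatment CT at Cycle 2, Days 15 to 21.

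- Cycle 2 Day 1 is study day 22, so the scan falls on study days 22+14 = 36 to 22+20 = 42.
- With the 3-week cycle delay that Protocol 9.2 allows, Cycle 2 Day 1 is study day 43 and the scan falls on days 57 to 63.
- Imaging for suspected progression, or an assessment at safety follow-up, may come earlier, but the protocol asks for these only where feasible.

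**Effect of k unevaluated deaths.** Let n be the cohort size (SAP 6.0: 22 HL, 8 sALCL) and e the number of later events. Assume no other censoring. After all k deaths:

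- deaths counted as events: S = (n-k-e)/n
- literal fallback: S = (n-k-e)/(n-k)
- ratio, correct to literal: (n-k)/n

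For k = 1:

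| Cohort | n | Ratio |
|---|---|---|
| sALCL | 8 | 7/8 = 0.875 |
| HL | 22 | 21/22 = 0.955 |
| All patients | 30 | 29/30 = 0.967 |

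Protocol 10.6 allows replacement where "Patient is not response evaluable according to the Revised Response Criteria for Malignant Lymphoma". A replaced patient with measurable lesions and one dose still meets the mITT definition, so n could become 9 or 23. The ratios are then 8/9 = 0.889 and 22/23 = 0.957.

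**Illustrations (the event counts are assumed).**

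- sALCL, n = 8, one unevaluated death, 3 later events: 4/8 = 50.0% correct, 4/7 = 57.1% literal, a difference of +7.1 points.
- HL, n = 22, one unevaluated death, 9 later events: 12/22 = 54.5% correct, 12/21 = 57.1% literal, +2.6 points.

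**Direction.** Take n = 8, a progression on day 20 and an unevaluated death on day 35 (both days assumed).

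- Days 20 to 34: 7/8 = 87.5% correct, 6/7 = 85.7% literal, -1.8 points.
- From day 35: 6/8 = 75.0% correct, 6/7 = 85.7% literal, +10.7 points.

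So the literal rule overstates PFS from the death onward. It can understate PFS slightly before the death if another event comes first.

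**The case against.** The strongest reply is that SAP 7.1 already settles who is censored: only subjects with no specified event. Section 7.8 then supplies the date. Death is a specified PFS event, so a dead patient never reaches the fallback. The paragraph supports this. The preceding rule censors at the last lesion assessment, a date that does not exist for a patient never assessed, and the fallback naturally supplies a default. This largely stands, and it is why the point is minor. What remains is that 7.1 sends the reader to 7.8 for the rule, and the sentence found there lacks the condition that the OS rule carries.

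It is also fair that the effect is confined. PFS is secondary, and the efficacy analyses are descriptive. ORR, CR rate, DOR and OS are untouched. Deaths are listed by subject and efficacy data by patient, so a miscensored case could be found, though a listing would not correct the curve. Entry requires ECOG 0 or 1, and "Survival for 3 or more months must be expected", which makes such deaths less likely without excluding them.

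A reader might infer that the SAP means to discard early deaths, or that the reported PFS will be inflated. The documents support neither: both PFS definitions and 7.1 point the other way, and no frequency of deaths before evaluation is given.

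A reader might also conclude that every death before the first evaluation must count as an event. That would contradict the same paragraph. A patient who stops before the first scan, starts other antitumor treatment and dies months later falls under the new-treatment censoring rule.

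**Conclusion.** The conflict is real but minor. Read literally, the fallback censors at time zero a dosed mITT patient who dies before any tumor evaluation, against the SAP's own PFS definition, SAP 7.1 and Protocol 14.1.3. The intended reading can be recovered from 7.1, so the wording does not show a wrong intention.

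The result differs only if such a death occurs and the sentence is programmed literally. For one death the correct curve is then 0.875 (n = 8) or 0.955 (n = 22) times the literal one, from that death onward. This assumes no other censoring and that the patient had not started other antitumor treatment. How often this would happen cannot be estimated from the documents.

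**What to change.** Replace the fallback sentence in SAP 7.8.2, before database lock, with:

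> Patients who have no tumor response evaluation after the first dose and no PFS event will be censored at the day of first dose. Death before any post-dose tumor evaluation is a PFS event on the date of death, unless the patient started antitumor treatment other than study drug or SCT before death; in that case the new-treatment censoring rule above applies, and the patient is censored at the day of first dose.

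The exception keeps the new text consistent with the existing new-treatment rule. The cost is one edit and no new data: deaths are already followed for OS (Protocol 10.9), and later anticancer therapies are already tabulated (SAP 7.6). The downside is a possibly less favourable PFS estimate.
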